We will recruit obese and normal weight subjects who are in early puberty as determined by Tanner staging of breast development and pubic hair in girls and by Tanner staging of pubic hair and estimation of testicular size in the boys. Adolescents whose pubertal status is at least Tanner II (T2), but no more than Tanner III (T3) will be asked to participate. In two studies that assessed insulin sensitivity across all stages of puberty, it was already significantly decreased from prepubertal insulin sensitivity at T2 and, while it had not yet completely recovered in early T5, it was still significantly increased from T4 insulin sensitivity (11;16). We will recruit through our metabolic syndrome and Good Life clinics, through advertisements, and from local pediatric clinics, including Denver Health Medical Center. Because of the ethnic make-up of our clinics, there will be Spanish-speaking only participants included in the study. The study coordinator is a native Spanish-speaker and, therefore, has the ability to consent the participants in Spanish using our consent and HIPAA forms that have been translated into Spanish. Lifestyle intervention materials are also available in Spanish. When the study coordinator is not available, an official Spanish interpreter will be used for the consent process and all study visits. Because of the anticipated high screen-failure rates due to failure to meet physical examination criteria (most notable Tanner staging criteria and BMI criteria), we will need to consent at least 40% more participants than we ultimately intend to enroll. Therefore, we anticipate that 225 participants will need to be consented for screening to be able to enroll 156 participants. The timeline of our experimental approach is shown below (Fig 2). A fasting baseline screening visit, to be performed at the pediatric Clinical Translational Research Center (CTRC), will include assessment of obesity status as determined by height, weight, BMI, waist circumference and hip circumference. An OGTT will be performed in all obese subjects to rule out IGT, IFG and diabetes in all subjects. The following screening labs will also be performed to examine for any significant underlying illness: AST, ALT, electrolytes, CBC, BUN, creatinine, lipids, and urinalysis.

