β -cell function will be preserved. This would make puberty a potential treatment period to target prevention of T2DM.

DESIGN

Participants:

1. 104 Obese participants:
 - a.) BMI \geq 95th percentile
 - b.) Tanner stage II – III at baseline
 - c.) Age \geq 9 years
 - d.) Absence of impaired glucose tolerance (IGT), impaired fasting glucose (IFG) or T2DM, as determined by oral glucose tolerance test (OGTT)

Exclusion criteria:

See Specific Aim 1

Approach:

All obese subjects who are recruited will be randomized after Study Visit 1 to receive metformin or placebo. The 52 participants randomized to the placebo group will then also serve as the obese subjects for the longitudinal observational studies of Specific Aim 1 (Please see Fig 2 for further clarification). In other words, 52 obese participants will be included in both Specific Aims 1 and 2, in order to minimize the total number of participants needed. Randomization will be stratified by: 1) Family history in a first degree relative with T2DM or no family history and 2) BMI between the 95th and 99th percentile or BMI greater than the 99th percentile. The extended release metformin will be started at 500 mg daily for one week and then increased by 500 mg a week until the target dose of 2000 mg a day is attained. The extended release preparation allows patients to take the medication once a day to promote improved adherence and is better tolerated. All obese participants will receive standard lifestyle counseling, focusing primarily on dietary improvements and increased physical activity. The total treatment period will be two years to include, on average, the most resistant stages of puberty. In order to monitor metformin compliance closely, the participants will come in for monthly pill-counts. In addition, each participant will be provided with a pill dispenser and a calendar to record each dose that is taken to assist with and track compliance. Furthermore, parents will be encouraged to remind the participant to take his/her medication. Participants will be given a point each time they bring in their pill bottle, whether or not they have been compliant, and will be eligible for an extra gift card for every 6 points they obtain. Our group has extensive experience in maintaining metformin compliance in this population (52). Tanner staging, anthropometric measurements and lifestyle counseling will also be performed at quarterly visits.

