Sample size calculation: A recruitment goal of 52 participants per group has been set (normal weight controls, obese controls, obese on metformin—a total of 156 participants). Assuming a 30% drop-out rate, this will give a final sample size of 30 per group. Power was run in PASS (NCSS Software; Kayesville, UT) and was calculated using a one-way ANOVA with a two-sided significance level of 0.05. Variability of the estimates was based on data available in an article by Buchanan et al. (57) in which IVGTT insulin sensitivity was measured in high-risk Hispanic women at baseline and 3 months for a placebo (n=109) and a troglitazone group (n=108). The 3-month change was -0.17 and 1.16 min^{-1} per $\mu\text{U}/\text{ml} \times 10^{-4}$, for the placebo and treatment groups, respectively. Assuming a correlation of 0.5, the estimated overall standard deviation of the 3-month change for both the placebo and treatment groups was 1.85 min^{-1} per $\mu\text{U}/\text{ml} \times 10^{-4}$. For this study, we assume similar variability and expect the 2-year change for the obese control and metformin groups to also be similar to those seen in the Buchanan et al. groups. The 2-year insulin sensitivity change in normal controls is expected to be similar to the change seen in Ball et al. (11) for 46 white adolescents from Tanner II / Tanner III to Tanner V, which was 1.6 min^{-1} per $\mu\text{U}/\text{ml} \times 10^{-4}$. Therefore, with a standard deviation of 1.85 and expected 2-year changes of 1.16, -0.17 and 1.6 for the metformin, obese control and normal control groups, respectively, a sample size of 30 per group achieves 93% power to detect an overall difference between the groups.

Statistical analysis: All analyses will assume a two-sided test of hypothesis with an overall significance level of 0.05 and will be performed in either SAS v9.1.3 or above (SAS Institute, Inc., Cary NC) or Splus v7.0 or above (Insightful Corp, Seattle WA).

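### A 30% drop-out from 52 per group leaves 36 completers, not 30, so recruitment, attrition and the sample size used for power do not agree

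*Combined protocol and SAP*

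**What the plan says.** The figures stand together in Section D, under Sample size calculation.

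- Recruitment: "A recruitment goal of 52 participants per group has been set", for normal weight controls, obese controls and obese on metformin, 156 in total.
- Attrition: "Assuming a 30% drop-out rate, this will give a final sample size of 30 per group".
- Test: power was "calculated using a one-way ANOVA with a two-sided significance level of 0.05".
- Inputs: "with a standard deviation of 1.85 and expected 2-year changes of 1.16, -0.17 and 1.6" for metformin, obese controls and normal controls respectively.
- Result: "a sample size of 30 per group achieves 93% power to detect an overall difference between the groups".

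The recruitment figure is used consistently elsewhere. The participant lists give 104 obese and 52 normal weight participants. The Approach under Specific Aim 1 says "we anticipate that 225 participants will need to be consented for screening to be able to enroll 156 participants". The Approach under Specific Aim 2 says "The 52 participants randomized to the placebo group will then also serve as the obese subjects for the longitudinal observational studies".

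**The concern.** The paragraph gives a starting number, a loss rate and a finishing number. Any two of them fix the third, and the three given do not fit together.

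The finishing number is the one the power calculation uses. As written, it is unclear whether the trial is meant to withstand 30% or 42% loss. That matters in a study of about two years for lean participants and about two and a half for obese participants, which names attrition among its own limitations. A data monitor seeing 38% loss, for example, could not say whether the trial was inside or outside its planning assumptions.

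There is also a question of justification. If 30 completers and 30% loss are what was intended, the enrolment target exceeds what those assumptions require, in children who undergo repeated IVGTTs.

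**Working it through.** **Inputs.** All come from the Sample size calculation: 52 recruited per group, 30% drop-out, 30 completers per group, three groups, means 1.16, -0.17 and 1.6, SD 1.85, alpha 0.05.

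**Step 1: reproduce the stated power at 30 per group.**

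- Grand mean = (1.16 - 0.17 + 1.6) / 3 = 0.863.
- Sum of squared deviations = 0.297² + (-1.033)² + 0.737² = 1.698.
- Noncentrality = n × 1.698 / 1.85² = n × 0.4963. At n = 30 this is 14.89.
- Power of the one-way ANOVA (noncentral F, 2 and 87 degrees of freedom) = 93.5%.

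This agrees with the stated 93%, so the power figure and the 30 belong together.

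**Step 2: check the link from recruits to completers.**

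| Two figures held | Formula | Third figure implied | Plan states |
|---|---|---|---|
| 52 recruited, 30% loss | 52 × (1 - 0.30) | 36.4, so 36 completers | 30 |
| 52 recruited, 30 completers | 1 - 30/52 | 42.3% loss | 30% |
| 30 completers, 30% loss | 30 / 0.70 = 42.9 | 43 recruited | 52 |

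In total, 30% loss leaves 3 × 36 = 108 completers (156 × 0.70 = 109.2 before rounding by group), against 3 × 30 = 90. With 43 per group, enrolment would be 3 × 43 = 129, and 156 - 129 = 27.

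**Step 3: look for another convention that gives the stated figures.**

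- Dividing by 1.3: 52 / 1.3 = 40 completers.
- Multiplying up from 30: 30 × 1.3 = 39 recruits, not 52.
- Applying 30% loss twice: 52 × 0.7 × 0.7 = 25.5 completers.

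None fits.

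**Step 4: look for a second source of loss.**

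- Screen failure is allowed for before enrolment (225 consented for 156 enrolled), so it cannot reduce the 52.
- Up to 10 obese pilot subjects sit outside the treatment arm (Approach, Specific Aim 1). Assume all 10 come out of the 104, which the plan does not say. Then (104 - 10) / 2 = 47 per obese arm, and 47 × 0.70 = 32.9. That is still not 30, and the normal weight group stays at 36.
- The limitations section discusses attrition but gives no rate.

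**Step 5: what 30 or 36 completers means for power.**

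The overall test uses Step 1's formula; at n = 36 the noncentrality is 17.87. The pairwise figures are unadjusted two-sided two-sample t-tests at 0.05, with noncentrality difference / (1.85 × √(2/n)). The differences are 1.16 + 0.17 = 1.33 (metformin against obese controls) and 1.6 + 0.17 = 1.77 (normal against obese controls).

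| Completers per group | Overall ANOVA | Metformin vs obese controls | Normal vs obese controls |
|---|---|---|---|
| 30 | 93.5% | 78.2% | 95.4% |
| 36 | 97.0% | 85.3% | 97.9% |

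On the same inputs, the metformin comparison needs 32 completers per arm for 80% power, so 30 falls just below that level and 36 is above it.

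**The case against.** The best defence is that nothing downstream is harmed. The 93% is correctly computed for the sample size to which it is attached. If 52 and 30% are right, the trial is better powered than claimed. If 30 is right, the claimed power stands and only the percentage is wrong. Either correction that keeps 52 recruits leaves overall power at 93% or more. This stands, and it limits the seriousness of the point: power is misstated only if 36 was the intended number, and then it is understated.

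A second argument is that the excess of 27 children should not be pressed. The plan never calls 30 a minimum, and recruiting 43 per group would leave the metformin comparison at 78%. This also largely stands. The excess follows only if 30 completers is taken as the requirement, and it is no reason to cut enrolment. It is a reason to justify 156 with figures that agree.

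A third argument is that pairwise power is a separate matter, since the plan states power only for the overall test. The strictly attributable change in the stated quantity is indeed 93.5% to 97.0%. However, the Statistical analysis paragraph tests both aims by pairwise contrasts, so the choice between 30 and 36 has its practical effect there.

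None of these arguments reconciles the three numbers.

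**Conclusion.** The concern holds. Recruiting 52, losing 30% and finishing with 30 cannot all be true: 30% loss leaves 36, and 30 completers means 42% loss. The documents do not show which figure is the slip.

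If recruitment and the loss rate are right, the completer number is understated by 6 per group. Overall power is then 97.0% instead of 93%, and power for metformin against obese controls is 85% instead of 78%. If 30 completers is right, the power statement stands and the tolerated attrition is 42%.

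The power figures rest on the plan's own means and SD, equal group sizes, and analysis of completers without covariates. The error is conservative on the first reading and does not threaten the trial. It should still be corrected, because the final sample size supports the only power claim and is part of the case for enrolling 156 children.

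**What to change.** Keep 52 per group and rewrite the attrition sentence in one of two ways:

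- State that 30% drop-out leaves 36 per group, and recompute power at 36: about 97% overall, about 85% for metformin against obese controls, about 98% for normal against obese controls.
- State that the design allows for up to 42% attrition, leaving 30 per group, and give power at 30: 93% overall, about 78% and about 95% for the two comparisons.

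The choice should follow the retention the investigators realistically expect. The same completer number should then be used wherever sample size or power is mentioned. If the obese pilot subjects count towards the 104, the sentence should say so, because the obese arms would then start below 52.

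The cost is one sentence and a recomputed power figure. Enrolment, randomisation, visits and analysis are unchanged.

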Simple descriptive statistics will be calculated for all variables (mean, median, standard deviation, minimum and maximum values for continuous variables; number and percentage of subjects for categorical variables). Linear regression will be used to compare 2-year change in insulin sensitivity, insulin secretion, and DI between groups for Specific Aims 1 and 2 (normal controls vs. obese controls and obese treated vs. obese controls). Potential confounders such as sex, 2-year change in percent body fat and 2-year change in BMI will be included in each model. In order to determine if the benefit of treatment persists beyond stopping treatment, the above analysis will be repeated on the change from baseline to 6 months post-treatment for the obese treated and obese control groups only. The mean change in each outcome from treatment stoppage to 6 months post treatment will also be calculated with 95% confidence intervals (CI) in order to assess maintenance of the level of each outcome. Although we are not powered for equivalence (to test the hypothesis that the 6-month change is equal to zero), the precision of the estimate and whether the difference is *clinically* significant will be evident from the 95% CI. A CTRC biostatistician will be available to consult on all matters of statistics.

Potential Difficulties and Limitations/Alternatives

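### The stated 93% power belongs to a three-group overall test that the plan never runs; the randomised metformin-placebo comparison has about 78% at the same 30 per group

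*Combined protocol and SAP*

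**What the plan says.** The Sample size calculation paragraph in section D sets three groups: "A recruitment goal of 52 participants per group has been set". It then gives the number expected to finish: "Assuming a 30% drop-out rate, this will give a final sample size of 30 per group". Power "was calculated using a one-way ANOVA with a two-sided significance level of 0.05". The inputs are for change in insulin sensitivity, in the document's units: "with a standard deviation of 1.85 and expected 2-year changes of 1.16, -0.17 and 1.6 for the metformin, obese control and normal control groups". The conclusion drawn is that "a sample size of 30 per group achieves 93% power to detect an overall difference between the groups".

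The Statistical analysis paragraph that follows plans something different: "Linear regression will be used to compare 2-year change in insulin sensitivity, insulin secretion, and DI between groups for Specific Aims 1 and 2". The comparisons are listed in brackets as "normal controls vs. obese controls and obese treated vs. obese controls". No three-group test appears, either as an analysis or as a gate before the pairwise comparisons, and neither comparison has a stated power.

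Under Specific Aim 2, obese participants are randomised to metformin or placebo after Study Visit 1. The placebo group also serves as the obese control group for Aim 1.

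**The concern.** An overall F-test asks whether any of the three means differ. Here the largest expected gap is between normal-weight and obese controls (1.6 against -0.17). That comparison is observational and does not involve metformin. A power figure drawn mainly from that gap can look comfortable while the drug comparison is much weaker.

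Metformin versus placebo is the only randomised question in the study and the only test of Hypothesis 2. Someone reading 93% will take it as the chance of detecting the drug effect the investigators expect. If the true chance is lower, the risk of missing that effect is understated, and a null result would be over-read as evidence against metformin.

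**Working it through.** **Inputs**, all from the Sample size calculation paragraph: expected changes of 1.16 (metformin), -0.17 (obese control) and 1.6 (normal control); SD 1.85; n = 30 per group; two-sided alpha 0.05.

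**1. Reproduce the stated figure.**
- Mean of the three changes: (1.16 - 0.17 + 1.6)/3 = 0.863.
- Sum of squared deviations: 0.297² + 1.033² + 0.737² = 1.698.
- Noncentrality: λ = n × Σ(m - mean)² / SD² = 30 × 1.698 / 1.85² = 14.89, on 2 and 87 degrees of freedom.
- Power from the noncentral F distribution: **93.5%**. The stated 93% reproduces, so the powered test is the three-group overall F-test.

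**2. Power of the comparisons actually planned** (two-sample t-test, noncentral t, 58 df, ncp = difference / (SD × √(2/n))).
- Metformin versus obese control: difference 1.16 - (-0.17) = 1.33; standardised 1.33/1.85 = 0.719; ncp = 2.78. Power **78.2%** (78.6% with the three-group error df of 87; 79.5% by normal approximation).
- Normal versus obese control: difference 1.6 - (-0.17) = 1.77; ncp = 3.71. Power **95.4%**.
- Both significant, by simulation: about 76 to 77%.

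**3. What drives the 93%.** The sum of squared deviations equals one third of the summed squared pairwise differences: (1.77² + 1.33² + 0.44²)/3 = (3.133 + 1.769 + 0.194)/3 = 1.698. The shares are:
- normal versus obese controls, 61%;
- metformin versus obese controls, 35%;
- normal versus metformin, 4%.

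**4. The overall test if metformin has no effect.** With changes of -0.17, -0.17 and 1.6, the sum of squared deviations is 2.089 and λ = 30 × 2.089 / 1.85² = 18.31. Power is **97.2%**. The powered test rejects more often when metformin is inert than under the planned effect.

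**5. What a given power would need for metformin versus placebo.**
- At 30 per arm, solving the formula in step 2 for the difference: 80% power needs 1.36 and 93% needs 1.67, against the planned 1.33.
- At the planned 1.33: 80% needs 32 evaluable per arm, 90% needs 42 and 93% needs 47.

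**6. Sensitivity.**
- Number finishing: 52 × 0.70 = 36.4, not 30 (30 of 52 would be a 42% loss).
- Alpha: the analysis paragraph sets an overall level of 0.05 without dividing it between comparisons. An equal split to 0.025 each is an assumption made here.

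| Power | n = 30 | n = 36 |
|---|---|---|
| Overall three-group F-test | 93.5% | 97.0% |
| Metformin vs obese control, alpha 0.05 | 78.2% | 85.3% |
| Normal vs obese control, alpha 0.05 | 95.4% | 97.9% |
| Metformin vs obese control, alpha 0.025 | 68.5% | 77.4% |

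**The case against.** The strongest reply is that nothing is miscalculated. The 93% is correct for the test named, the document describes it accurately as power for an overall difference, and it never claims 93% for Aim 2. This stands as a description: the fault is a mismatch between the powered test and the planned tests, not an arithmetic slip. It does not rescue the figure, because no planned analysis uses that test and the tests that are planned have no stated power.

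A second reply is that 78% is nearly 80%, and that with 36 finishing per arm the comparison passes 80%. Both statements are true. The shortfall from 80% is under 2 points and depends on the document's own 30, which disagrees with its recruitment and drop-out figures. The gap that matters is the one between 93% and the power of the randomised test: about 15 points at n = 30, and about 12 points at n = 36 (97.0% against 85.3%).

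Third, the planned models include sex and the two-year changes in percent body fat and BMI, so an unadjusted t-test is only an approximation to them. This is a fair limit. Adjustment could reduce residual variance. Metformin could also affect body fat and BMI, in which case adjusting for their changes could shrink the estimated effect. The documents give no figures for either, so neither gain nor loss can be assumed.

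Finally, the 97% rejection rate under an inert drug describes a test that the plan does not run, and Hypothesis 2 does have its own planned comparison. That is correct. The 97% shows only why the overall test's power cannot stand in for that comparison's power.

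**Conclusion.** The concern holds. The only power figure in the plan describes a test that is not in its analysis. On the plan's own inputs at 30 per group, the randomised comparison has about 78% power, so the chance of missing the expected metformin effect is about 22% rather than the 7% a reader would infer. The Aim 1 comparison is adequately powered at about 95%.

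These figures accept the difference of 1.33 and the SD of 1.85 as given, use 30 evaluable per group, are unadjusted for covariates, and spend 0.05 on each comparison. With 36 per group the metformin figure rises to about 85%. With an equal alpha split it falls to 68.5% (n = 30) or 77.4% (n = 36). In none of these cases does it reach 93%.

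**What to change.** In the Sample size calculation paragraph, replace the overall-difference statement with power for the two planned comparisons, labelled as unadjusted two-sample figures at two-sided 0.05 each:

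- With 30 completers per group: about 78% for metformin versus placebo (difference 1.33) and about 95% for normal versus obese controls (difference 1.77).
- If the completer number is corrected to 36: about 85% and 98%.

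State the detectable metformin-placebo difference beside these, which is 1.36 for 80% power at 30 per arm. Say whether the overall 0.05 is divided between the two comparisons. If it is, give the power at the divided level instead.

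The cost is two or three sentences and a less favourable stated power for Aim 2. Enrolment, visits and the choice of comparisons stay as they are.

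### The plan claims an overall 0.05 level for nine planned tests but names no primary outcome and no method that would hold it

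*Combined protocol and SAP*

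**What the plan says.** All of this is in section D of the combined protocol and SAP, under Sample size calculation and Statistical analysis.

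- **Level.** "All analyses will assume a two-sided test of hypothesis with an overall significance level of 0.05". No level is given for any single test.
- **Outcomes.** "Linear regression will be used to compare 2-year change in insulin sensitivity, insulin secretion, and DI between groups for Specific Aims 1 and 2". The three are listed side by side and none is called primary.
- **Comparisons.** "normal controls vs. obese controls and obese treated vs. obese controls". Both use the obese control group.
- **Post-treatment repeat.** "the above analysis will be repeated on the change from baseline to 6 months post-treatment for the obese treated and obese control groups only".
- **Off-treatment change.** The mean change from stopping treatment to six months later "will also be calculated with 95% confidence intervals (CI) in order to assess maintenance of the level of each outcome". This is estimation, and I do not count it as a test.
- **Power.** It "was calculated using a one-way ANOVA with a two-sided significance level of 0.05", for insulin sensitivity only, with "expected 2-year changes of 1.16, -0.17 and 1.6 for the metformin, obese control and normal control groups". The Statistical analysis paragraph does not include that three-group ANOVA.

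Aims 1b and 2b also promise comparisons of body composition, fat distribution and inflammatory markers. The regression plan does not list them, so they are left out of the count.

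**The concern.** An overall level is a promise about a set of tests taken together. To keep it, a plan needs a single primary test, an order of testing, a split of the level or a gatekeeping test. This plan has none of these. The ANOVA could have served as a gatekeeper for S_I, but it appears only in the power calculation.

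The randomised comparison has most at stake. Hypothesis 2 predicts better insulin sensitivity, less compensatory hyperinsulinemia, preserved secretion and better DI. With no primary outcome, metformin could be reported as effective on any of three outcomes at either of two times, under a statement that the overall error was 5%. AIR leaves further room: a fall might be read as less hyperinsulinemia and a rise as preserved secretion.

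**Working it through.** **1. The plan's own figure.** Inputs from Sample size calculation: mean changes 1.16, -0.17 and 1.6, SD 1.85, 30 per group.
- Grand mean = (1.16 - 0.17 + 1.6)/3 = 0.863. Sum of squared deviations = 1.698.
- Noncentrality = 30 × 1.698/1.85² = 14.89, with 2 and 87 degrees of freedom.
- Power = 93.5%, against 93% stated. It reproduces, but for one omnibus test on one outcome.

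**2. Count of tests.** End of treatment: 3 outcomes × 2 comparisons = 6. Six months after treatment: 3 outcomes × 1 comparison = 3. Total 9. Metformin against obese control accounts for 3 + 3 = 6 of them.

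**3. Chance of at least one false positive.** Conditions: every null hypothesis true, each test two-sided at 0.05, equal groups, shared obese controls. Under these conditions the large-sample result does not depend on group size.

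DI is computed from S_I and AIR, so the three outcomes cannot all be independent. I simulated S_I and AIR on the log scale with equal variance, took DI as their product (a sum of logs), and used 300,000 runs per setting. The assumed S_I-AIR correlation runs from 0 to -0.7, and the assumed correlation between the two times from 0.5 to 0.9.

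| Family of tests | Tests | At least one false positive |
|---|---|---|
| S_I only, one test per aim | 2 | about 9% |
| Metformin vs obese control, end of treatment | 3 | about 12% |
| Metformin vs obese control, both times | 6 | about 16-21% |
| Both aims, all tests | 9 | about 24-29% |

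*Sensitivity.* The Background describes DI as a ratio of sensitivity to secretion. Taken literally (a difference of logs), the last three rows become about 9-12%, 12-20% and 18-28%. If DI is not tied to the other two, and outcome correlations run from 0 to 0.9 and time correlations from 0 to 0.9, the six metformin tests give about 12-26% and all nine about 18-36%. Every version exceeds 5%.

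**4. If overall 0.05 is meant literally.** An equal split over nine tests gives 0.05/9 = 0.0056 per test. For metformin vs obese control on S_I, the difference is 1.16 - (-0.17) = 1.33 and the noncentrality is 1.33/(1.85 × √(2/30)) = 2.78. Power with 30 per group is 78% at 0.05 and 47% at 0.0056. The sample size makes no allowance for this.

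**The case against.** **The plan never says each test is run at 0.05.** True. The only level stated is the overall one, and the per-test reading is an inference. A reader might conclude that the trial's real overall error is 20-30%. The documents do not support that as a fact: it needs the per-test reading, assumed correlations, all nulls true, and both aims pooled. What remains is an overall level with no mechanism behind it.

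**Pooling the aims overstates the risk to the metformin claim.** This also stands. Aim 1 is a non-randomised comparison with its own hypothesis, and its three tests cannot produce a metformin claim. The metformin rows of the table are therefore the relevant ones, and they still exceed 5%.

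**The independent-test figures cannot occur.** A reader might reach for 1 - 0.95⁶ = 26% or 1 - 0.95⁹ = 37%. Since all three outcomes come from the same glucose tolerance test and DI is derived from the other two, neither describes this trial.

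**Insulin sensitivity is already the lead outcome.** In substance, yes. Hypothesis 1 concerns it alone, Hypothesis 2 puts it first, and the sample size uses nothing else. The six-month analysis asks whether a benefit persists, which arguably presupposes one at end of treatment. It would therefore be too strong to say that the plan treats the outcomes as equals. But the analysis text does not turn this emphasis into a rule, and it makes neither the other outcomes nor the six-month tests conditional on anything.

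**Conclusion.** The concern holds as a gap in the plan: an overall two-sided 0.05 is stated for nine tests, with no primary outcome, order, per-test level or adjustment to deliver it. If each test is run at 0.05 and nothing works, the chance of a false metformin finding is about 12% at end of treatment and about 16-21% over both times. For all nine tests across both aims it is about 24-29%. These sizes assume DI as the product of S_I and AIR and a time correlation of 0.5-0.9; the documents give no correlations, and other choices move the figures as shown above.

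A reader might also infer that the trial is underpowered or that a metformin result could not be trusted. This point shows neither. The stated omnibus power reproduces, and the S_I comparison at 0.05 is unaffected once S_I is designated. The plan should be corrected on this point, but the design need not change.

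**What to change.** 1. Name change in S_I from baseline to Tanner V as the single primary outcome of each aim, tested at two-sided 0.05. State the time point explicitly: the analysis text speaks of a two-year change, while the aims and the Potential Difficulties section tie the assessment to completion of puberty.
2. Label AIR, DI and all six-month post-treatment comparisons secondary. Report them with 95% confidence intervals and no confirmatory claim, which is how the plan already treats the off-treatment change. Alternatively, test them in an order that the investigators fix in advance. The documents do not settle that order. For example, DI before AIR could block the AIR test if secretion fully compensates and DI is maintained, a pattern the Background describes.
3. Replace the overall-level wording with *0.05 for the primary outcome of each aim*, and say openly that the two aims are treated as separate questions, with an error of about 9% across both.

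The cost is a few sentences. No participants are added, and power for S_I at 0.05 does not change (78% for metformin vs obese control at 30 per group on the plan's figures). The downside is that AIR, DI and six-month results can no longer stand alone as confirmatory.
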